2 STUDY SYNOPSIS

Title	A Prospective, Double-blind, Randomized, Placebo-controlled, Repeated dose, Multicentre Phase IIa Proof-of-Concept Study with BT063 in Subjects with Systemic Lupus Erythematosus (BT063 in SLE)
Clinical Phase	IIa
Coordinating Investigator	[REDACTED]
Study Objectives	
This study has 2 parts. The primary objective of Part I of this study is to evaluate the safety and tolerability of 3 months of treatment with 50 mg BT063 versus placebo in subjects with systemic lupus erythematosus (SLE).
 
The primary objective of Part II of this study is to evaluate the safety and tolerability of either 25 mg, 50 mg or 100 mg BT063 versus placebo in subjects with SLE. The dose level for Part II will be determined based on an interim analysis conducted after Part I.
 
Secondary objectives for both parts of the study are to:
 
 • Evaluate the efficacy of 3 months of treatment with BT063 versus placebo as assessed by various disease activity indices including subject-reported outcomes • Determine the pharmacokinetics (PK) of BT063 • Compare the pharmacodynamics (PD) of BT063 and placebo on various PD markers including biomarkers • Determine the immunogenicity of BT063
Study Design	Prospective, double-blind, randomized, placebo-controlled, multicentre, proof-of-concept study conducted in 2 parts; including an interim analysis at the end of Part I. Subjects who participate in Part I of the study cannot participate in Part II
Study Population	Subjects with active SLE disease
Inclusion Criteria	
 • Able to provide written informed consent and/or consent obtained from a legally acceptable representative (as required by Institutional Review Board/Independent Ethics Committee) prior to the initiation of any protocol-required procedures • Diagnosis of SLE as defined by American College of Rheumatology (ACR) criteria such that ≥ 4 of the 11 criteria are met for ≥ 3 months before screening • Moderate to severe SLE disease activity at screening and baseline demonstrated by SLEDAI-2K total score

	
≥ 6, including skin and joint involvement
 
Regarding skin and joints, both need to be involved, and either skin should be involved according to CLASI Activity score ≥ 5 or at least 5 of 66/68 joints with pain and signs of inflammation present at screening and baseline (joints suspected or known to have ischemic osteonecrosis are not to be taken into consideration)No change in concomitant medication for SLE activity maintenance and symptom control (e.g., azathioprine, methotrexate, leflunomide, mycophenolate mofetil, cyclosporine, antimalarials such as chloroquine or hydroxychloroquine, glucocorticosteroids, pain medication, e.g. nonsteroidal anti-inflammatory drugs [NSAIDs] or paracetamol) regarding type of medication and dose level for at least 8 weeks prior to baseline (for steroids and NSAIDs/pain medication 2 weeks) and with the expectation that there will be no need for change in concomitant medication until the End-of-Treatment visit (ideally throughout the whole study); however, if the subject is taking an oral glucocorticosteroid at a dose higher than equivalent to 20 mg prednisone/day, and planning to reduce dose of glucocorticosteroid, the dose can be titrated down during the screening period so that the subject has been on, at most, a dose equivalent to 20 mg prednisone/day for 2 weeks by day 0 (baseline; i.e., first BT063 dose)The dose of concomitant medication for SLE activity maintenance and symptom control (e.g., azathioprine, methotrexate, leflunomide, mycophenolate mofetil, cyclosporine, antimalarials such as chloroquine or hydroxychloroquine, glucocorticosteroids, pain medication, e.g. nonsteroidal anti-inflammatory drugs [NSAIDs] or paracetamol) should not exceed the doses outlined in the summary of product characteristics (SPC) or standards for SLE management. For oral glucocorticosteroids maximal allowed dose is limited to a dose equivalent to 20 mg prednisone/day. NSAIDs should not be taken within 24 hours, paracetamol not within 12 hours prior to study visitsPositive anti-nuclear antibodies (ANA) test at screening (as per central laboratory results).Age ≥ 18 and ≤ 75 years at screeningBody mass index ≥ 18 and ≤ 35 kg/m²Normal electrocardiogram (ECG), i.e., no acute and clinically relevant abnormalities
--	---

Exclusion Criteria	
Has active, severe SLE disease activity which involves the renal system and/or active, severe, neuropsychiatric SLE, defined as any neuropsychiatric element scoring BILAG level A diseaseDiagnosed psoriasisPresence or history of malignancy within the previous 5 years (except successfully treated non-metastatic cutaneous squamous or basal cell carcinoma and/or localized carcinoma in situ of the cervix)Received any vaccination within 8 weeks prior to screening (except for influenza or tetanus booster)History of more than 3 infections during the last 12 months, requiring intravenous (IV) antibiotic treatmentSystemic antibiotic treatment within 2 weeks before baseline visitA positive diagnosis for any of the following:
Acute or chronic viral hepatitis B (isolated positivity to hepatitis B surface antibody [anti-HBs] is allowed as an indicator of a previous vaccination that will be confirmed in subject's notes) or acute or chronic hepatitis C (positive to anti-hepatitis C antibodies or hepatitis C viral RNA)Human immunodeficiency virus (HIV) or tested positive for tuberculosis as assessed by QuantiFERON® TB gold test (if the result is inconclusive it may be repeated once)Acute, clinically relevant, or potentially recent infection with Herpes Zoster or Herpes Simplex (Type 1 and Type 2), Epstein-Barr virus (EBV) or cytomegalovirus (CMV) infection or reactivation at screeningClinically significant hematologic abnormalities attributed to SLE:
Haemoglobin < 8 g/dLPlatelets < 50 × 10⁹/LLeucocytes < 2.0 × 10⁹/LActive or history of inflammatory bowel disease (including active or history of colitis)Received the following medications:
Rituximab within the last 48 weeks before screeningBelimumab within the last 12 weeks before screeningIV immunoglobulin (Ig) within the last 12 weeks before screening
---------------------------	--

	
○ Intramuscular (IM) or intra-articular glucocorticosteroids within the last 4 weeks before screening○ IV cyclophosphamide within the last 6 months before screening○ IV glucocorticosteroids (pulse therapy) within the last 6 months before screening● Participation in another clinical study in the 90 days prior to baseline or within 5 half-lives of the investigated compound, whichever is longer; Participation in another clinical study during this study and/or previous participation in this study● Pregnant or nursing women or women who intend to become pregnant● Men or women not willing to use effective contraception excluding women not of childbearing potential (Subjects who are sexually active women of childbearing potential or sexually active men who are not practicing 2 different methods of birth control with their partner during the trial and for 4 months after the last dose of IMP or who will not remain abstinent during the trial and for 4 months after the last dose. If using birth control, each couple must use 2 of the following precautions: vasectomy, tubal ligation, vaginal diaphragm, intrauterine device, birth control pill, birth control implant, birth control depot injections, condom, or sponge with spermicide. Women who are not of childbearing potential include those who are at least 1 year post-menopausal confirmed by follicle-stimulating hormone levels or women who are surgically sterile)● Known intolerance to immunoglobulins or comparable substances (e.g., significant vaccination reaction)● Known intolerance to proteins of human origin● Employee or direct relative of an employee of the contract research organization (CRO), the study site, or Biostest● History of clinically significant drug or alcohol abuse within the last 12 months● Any other significant acute or chronic illness or laboratory abnormality, which, in the opinion of the investigator, might compromise the safety of the subject or influence the outcome of the study and its objectives
--	--

Number of Subjects	Part I: Placebo, n= 6 BT063, n=12 Part II (depending on interim analysis): Placebo, n= 6 BT063, n=12
Countries/Number of Study Sites	3 to 4 countries, 12 to 15 sites
Investigational Medicinal Product (IMP)	BT063 and matching placebo administered as IV infusion
Dosage and Mode of Administration	Part I: Placebo, or BT063 (50 mg) at week 0 (baseline), week 1, 2, 4, 6, 8, 10, and 12 Part II (depending on interim analysis results of Part I): Placebo, or BT063 (either 25 mg, 50 mg or 100 mg) at week 0 (baseline), week 1, 2, 4, 6, 8, 10, and 12
Duration of Treatment	3 months of treatment with 4 months of Follow-Up
Criteria for Evaluation Safety Assessments	
 • Adverse events (AEs), serious AEs (SAEs), and withdrawals due to AEs • Physical examinations • Vital signs • ECGs • Safety laboratory parameters (full blood count including white differential count, clinical chemistry, thyroid hormones, urinalysis, and faecal occult blood test) • Auto-antibodies against double-stranded DNA (anti-dsDNA) and nucleus (ANA), thyroid gland (thyroid peroxidase [TPO], thyroid stimulating hormone receptor [TSHR]), anti-islet cells, anti-cyclic citrullinated peptide (CCP), Coombs test • Anti-drug antibodies against BT063 (anti-BT063) • Immunological status of potential viral and bacterial infections (HBV, HCV, HIV, tetanus, diphtheria tuberculosis as well as EBV / CMV serology)

Efficacy Assessments	
 • Systemic Lupus Erythematosus Disease Activity Index 2000 (SLEDAI-2K) • Cutaneous Lupus Erythematosus Disease Area and Sensitivity Index (CLASI) • British Isles Lupus Assessment Group (BILAG) assessments • Tender/swollen joint counts • Physician's Assessment of Disease Activity (Physician's Global Assessment, PGA) • Subject Reported Outcomes using the Functional Assessment of Chronic Illness Therapy – Fatigue (FACIT-F), and SF-36v2 Physical Component Score (PCS) • European Consensus Lupus Activity Measurement (ECLAM) Pharmacokinetics and Pharmacodynamics 
 • Pharmacokinetics: BT063 serum concentration 
 - Maximum serum concentration (C_{max}) - Time to maximum serum concentration (t_{max}) - Area under the concentration-time curve from time 0 to the last observable concentration at time t (AUC_{0-t}) - Elimination half-life ($t_{1/2}$) - Apparent terminal-phase disposition rate constant (λ_z) - Total body clearance from serum (CL) - Apparent volume of distribution during the terminal phase (V_z) • Pharmacodynamics: 
 - T- and B-lymphocytes (CD3, CD4, CD8, CD19, CD20, CD27, CD38, CD69, CD62L, HLA DR, CD45RA) - Complement activity CH50, C3, and C4 - Erythrocyte sedimentation rate (ESR) and C-reactive protein (CRP) - Cytokines (IL-1β, IL-2, IL-4, IL-5, IL-6, IL-8, IL-10, TNF-α, IFN-γ) - Immunoglobulins (IgG, IgM, IgA, IgE) - Free IL-10 • Biomarkers related to IL-10 biology and expected safety, efficacy, and mechanism of action of BT063 • Immunological parameters
Endpoints 
 - Primary - Safety 	
 • Incidence of Adverse events (Including SAEs and AEs leading to discontinuation) from Baseline through End of Trial Visit (Week 14)


- Secondary – Efficacy
 
Pharmacokinetics and Pharmacodynamics
	
 • Changes from baseline through End of Trial Visit (Week 14) in: 
 ◦ Physical examinations ◦ Vital signs ◦ ECGs ◦ Safety laboratory parameters (full blood count including white differential count, clinical chemistry, thyroid hormones, urinalysis, and faecal occult blood test) ◦ Development of anti-drug antibodies against BT063 (anti-BT063) ◦ Immunological status of potential viral and bacterial infections (HBV, HCV, HIV, tetanus, diphtheria tuberculosis) ◦ EBV / CMV Serology ◦ Premature withdrawals • 50% improvement of swollen/tender joints or 50% improvement in CLASI Activity score at week 14 and week 28, depending on which was the more severe manifestation at baseline. • Percent changes in SLEDAI-2K scores from baseline to week 14 and at week 28 • Flare rate and severity at week 14 and week 28 based on BILAG index A or B (flare is defined as the presence of 1 or more new BILAG A scores or 2 or more new BILAG B scores.) • Time to first flare • Number of patients requiring an increase in oral glucocorticosteroid dose before week 14 • Physician's Global Assessment, Functional Assessment of Chronic Illness Therapy – Fatigue (FACIT-F) and SF-36v2 Physical Component Score (PCS) at week 14 and week 28 • ECLAM at week 14 and week 28 
Based on PK/PD findings at protocol-defined time points:
 
 • Pharmacokinetics: 
 - BT063 serum concentration - Maximum serum concentration (C_{max}) - Time to maximum serum concentration (t_{max}) - Area under the concentration-time curve from time 0 to the last observable concentration at time t (AUC_{0-t}) - Elimination half-life ($t_{1/2}$) - Apparent terminal-phase disposition rate constant (λ_z) - Total body clearance from serum (CL)
--	---

	
 - Apparent volume of distribution during the terminal phase (V_z). • Pharmacodynamics: 
 - T- and B-lymphocytes (CD3, CD4, CD8, CD19, CD20, CD27, CD38, CD69, CD62L, HLA DR, CD45RA) - Complement activity CH50, C3, and C4 - Erythrocyte sedimentation rate (ESR) and C-reactive protein - Cytokines (IL-1β, IL-2, IL-4, IL-5, IL-6, IL-8, IL-10, TNF-α, IFN-γ) - Immunoglobulins (IgG, IgM, IgA, IgE) - Free IL-10 • Biomarkers related to IL-10 biology and expected safety, efficacy, and mechanism of action of BT063 • Immunological parameters
Concomitant Medication	
Allowed
 
Stable background therapy with standard SLE medication (e.g. e.g., steroids, azathioprine, antimalarials such as chloroquine or hydroxychloroquine, methotrexate, leflunomide, mycophenolate mofetil, cyclosporine) should not exceed the doses outlined in the summary of product characteristics (SPC) or standards for SLE management.
 
Stable dose of oral glucocorticosteroids up to 20 mg/day. Topical non-steroidal treatment of skin lesions and analgesic treatment of joint pain is allowed; however, not within 24 hours before assessment
 
Prohibited
 
Prohibited within protocol-specified time frames
 
 • IV cyclophosphamide • IV glucocorticosteroids • Rituximab, belimumab • Investigational agents • IM or intra-articular administration of glucocorticosteroids • Plasmapheresis and/or IVIg therapy
Biometrical Concept	Explorative descriptive statistics will be used for all variables. No statistical tests will be performed.
Data and Safety Monitoring Board	An independent Data and Safety Monitoring Board (DSMB) will be established.
First Subject First Visit (planned)	May 2015
Last Subject Last Visit (planned)	Q3 2017

Confidentiality Statement

This protocol is the property of Biotest and may not be circulated, reproduced or published - either in whole or in part - without the company's written permission.

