11.1.3 Dose Justification

The dosing regimen for Study 990 is based on the results of the investigator-initiated trial with B-N10 (the murine predecessor of BT063) in subjects with SLE ([Llorente](#) et al 2000), a single-dose escalation Phase I study (Study 977) with BT063 in healthy subjects, a repeated-dose toxicity study in monkeys (Study BE-092-43/00), extrapolation of PD effects from *in vitro* whole blood assay, and the modelling and simulation of kinetic of plasma concentrations based on PK data from Study 977.

[Llorente](#) et al demonstrated that treatment of SLE subjects with daily IV doses of 20 mg B-N10 over 21 days led to an improvement of skin lesions and joint symptoms ([Llorente](#) et al 2000). Signs and symptoms started to improve by day 10 to 12, and optimal improvement was reached at month 2. At the end of the follow-up period of 6 months, the disease was clinically inactive in 5 of 6 subjects. The mean steady state plasma concentration of B-N10 during the treatment phase was 20 µg/mL (range: 14 to 27 µg/mL on day 9 to 11). Similarly, in this proof-of-concept study (Study 990), one objective is to demonstrate improvement of skin and/or joint symptoms by maintaining an average plasma concentration close to 20 µg/mL during 12 weeks IMP treatment. Signs and symptoms of SLE will be recorded for 16 weeks after treatment is completed (at an End of Treatment Visit 2 weeks after the last dose of IMP and then for an additional 14 weeks).

In Study 977, single IV doses of 0.175, 0.75, 3.5, 7.5, 15, 30, 60, and 100 mg BT063 were given to healthy subjects (12 male, 11 female). Overall, BT063 was well tolerated during this study. Most of the observed AEs were consistent to those seen in a healthy population, although mouth ulcers occurred in subjects starting at the 15 mg dose group. After recurrence of mouth ulcers 43 days after the 100 mg BT063 dose in the first subject of the 100 mg cohort, the Sponsor determined that the risks outweighed the benefits in healthy subjects, so the last subject of the 100 mg cohort was not dosed.

[figure not shown]
In addition to preliminary safety data, pharmacokinetic behaviour of BT063 was also examined in Study 977. The data showed that the maximum plasma concentration (C_{max}) was reached in humans 1 to 2 hours after IV dosing. The total exposure as

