13.1.12 End of Treatment/Early Termination – Visit 12, Day 98±2 (Week 14)

The following procedures will be completed at the End of Treatment/Early Termination Visit at the times designated on the Flowchart of the Study ([Section 3](#)).

- Record AEs
- Perform targeted physical examination (including weight)
- Measure and record vital signs (pulse, blood pressure, and body temperature)
- Perform 12-lead ECG
- Draw blood for safety laboratory assessments (haematology, coagulation, clinical chemistry), auto-antibodies (ANA, anti-dsDNA, thyroid gland [TPO and TSHR], anti-islet cells, anti-CCP, and Coombs test), anti-BT063 antibodies, immunological status, and EBV and CMV serology
- Draw additional blood for the following tests: TSH, fT3, fT4, fasting glucose, fasting triglycerides, fasting cholesterol, fasting high-density lipoprotein, and fasting low-density lipoprotein (fasting must be for at least 12 hours)
- Obtain sample for urinalysis and faecal occult blood
- Urine pregnancy test in women of childbearing potential
- Record concomitant medications
- Perform and record the following assessments:
 - Subject Reported Outcomes: FACIT-F and SF-36v2
 - SLEDAI-2K
 - CLASI Activity score
 - BILAG score
 - Tender joint count and swollen joint count
 - Physician's Global Assessment of Disease Activity
 - ECLAM

- Draw blood for PK and PD assessments: serum level of BT063, complement activity, ESR and CRP, cytokines, immunoglobulins, Free IL-10, and biomarkers

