13.1.13 Follow-up – Visit 13, Day 140±7 (Week 20)

The following procedures will be completed at the first Follow-up Visit at the times designated on the Flowchart of the Study ([Section 3](#)).

- Record AEs
- Perform targeted physical examination
- Measure and record vital signs (pulse, blood pressure, and body temperature)
- Draw blood for safety laboratory assessments (haematology, coagulation, and clinical chemistry), auto-antibodies (ANA, anti-dsDNA, thyroid gland [TPO and TSHR], anti-islet cells, anti-CCP, and Coombs test), and anti-BT063 antibodies
- Obtain sample for urinalysis
- Record concomitant medications
- Perform and record the following assessments:
 - Subject Reported Outcomes: FACIT-F and SF-36v2
 - SLEDAI-2K
 - CLASI Activity score
 - BILAG score
 - Tender joint count and swollen joint count
 - Physician's Global Assessment of Disease Activity
 - ECLAM
- Draw blood for PK and PD assessments: serum level of BT063, complement activity, ESR and CRP, Free IL-10.

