13.1.14 Follow-up - Visit 14, Day 196±7 (Week 28)

The following procedures will be completed at the second Follow-up Visit at the times designated on the Flowchart of the Study ([Section 3](#)).

- Record AEs
- Perform targeted physical examination
- Measure and record vital signs (pulse, blood pressure, and body temperature)
- Draw blood for safety laboratory assessments (haematology, coagulation, clinical chemistry), auto-antibodies (ANA, anti-dsDNA, thyroid gland [TPO and TSHR], anti-islet cells, anti-CCP, and Coombs test), and anti-BT063 antibodies; as well as retention samples for immunological status and EBV and CMV serology
- Obtain sample for urinalysis
- Record concomitant medications
- Perform and record the following assessments:
 - Subject Reported Outcomes: FACIT-F and SF-36v2
 - SLEDAI-2K
 - CLASI Activity score

- BILAG score
- Tender joint count and swollen joint count
- Physician's Global Assessment of Disease Activity
- ECLAM
- Draw blood for PK and PD assessments: serum level of BT063, T- and B-lymphocytes, complement activity, ESR and CRP, cytokines, Free IL-10, and biomarkers

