14.1.2 Methods for Assessing, Recording and Analysing Safety Parameter(s)

14.1.2.1 Adverse Events

Safety and tolerability will be addressed by occurrence, frequency, nature, and severity of AEs. Adverse event and SAE assessments will be made throughout the study and will be evaluated and recorded in the source documents and on the eCRF as specified in [Section 14.3.2](#).

The seriousness, severity, and causality of each AE or SAE will be evaluated by the investigator in accordance with the definitions in [Section 14.3.1](#).

Subjects will be asked about AEs that occurred during the IV infusion or since the last visit by the use of non-leading questions.

Adverse Events of Special Interest

Adverse Events of special interest (AESI; serious or nonserious) are events that are of scientific and medical concern specific to the Sponsor's product for which close monitoring and rapid communication by the investigator to the Sponsor is appropriate. For this study, the following AEs of special interest will be recorded:

- Aphthous mouth ulcers (new, recurrent or aggravation of pre-existing lesions)
- Any other GI ulcers or significant GI symptoms (e.g., pain, blood in stool, dyspepsia or similar)

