14.3 Adverse Events

14.3.1 Definitions

Adverse Event (AE)

Per ICH, an AE is defined as any untoward medical occurrence in a patient or clinical investigation subject administered a pharmaceutical product and which does not

necessarily have a causal relationship with this treatment. An AE can therefore be any unfavourable or unintended sign (including an abnormal laboratory finding), symptom, or disease temporally associated with the use of a medicinal (investigational) product, whether or not related to the medicinal (investigational) product. The AE may be any of the following:

- A new illness
- An exacerbation of a sign or symptom or the underlying condition or of a concomitant illness under treatment
- Unrelated to participation in the clinical study or an effect of the study medication or comparator drug
- A combination of 1 or more of the above factors

No causal relationship with the study medication is implied by the use of the term "adverse event."

Planned or elective surgical or invasive procedures for pre-existing conditions that have not worsened are not AEs. However, any complication that occurs during a planned or elective surgery is an AE. Conditions leading to unplanned surgical procedures may be AEs.

When an AE occurs after written consent has been obtained but before the first dose of study drug, the AE will be considered a non-treatment emergent AE. An AE that occurs from the time the subject receives his/her first dose of study drug until his/her last study visit will be considered a treatment-emergent AE regardless of the assessed relationship to the administration of the IMP.

For the recording of pregnancy and relevant laboratory data see [Section 14.3.2](#).

Immediately Reportable Adverse Event

Immediately reportable AEs (IRAEs) are AEs that must be reported to the Sponsor within 24 hours of the study site being informed of the IRAE (reporting requirements are detailed in [Section 14.3.2.1](#)).

Immediately reportable AEs include:

- All SAEs
- Overdose
- Pregnancy
- AEs that result in a subject's withdrawal from the study
- All AESIs ([Section 14.1.2.1](#))

Serious adverse event (SAE)

An SAE is any untoward medical occurrence or effect that at any dose:

- Results in death

- *Death is an outcome of an AE and not an AE in itself. All deaths, regardless of cause or relationship must be reported for subjects on study.*
- Is life-threatening

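### The primary safety endpoint closes at an End of Trial Visit (Week 14) that the schedule does not contain: Week 14 is End of Treatment, and as worded the endpoint stops 98 days before the treatment-emergent period ends

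*Protocol*

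**What the plan says.** **Endpoint.** Section 2 (Study Synopsis, Endpoints) gives the primary safety endpoint as "Incidence of Adverse events (Including SAEs and AEs leading to discontinuation) from Baseline through End of Trial Visit (Week 14"). The next entry repeats the closing visit for the remaining safety endpoints: "Changes from baseline through End of Trial Visit (Week 14) in" a list that includes development of anti-BT063 antibodies. The efficacy endpoints that follow mostly name Week 14 and Week 28 separately.

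**Schedule.** Section 13.1.12 heads Week 14, Day 98±2, as Visit 12: "The following procedures will be completed at the End of Treatment/Early Termination Visit at the times designated". Two follow-up visits come after it: Visit 13 at Day 140 (Week 20) and Visit 14 at Day 196 (Week 28). Section 13.2.1 defines the end of study as the last subject's last visit.

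**Adverse events.** Section 14.3.1 says that an event "from the time the subject receives his/her first dose of study drug until his/her last study visit will be considered a treatment-emergent AE". Section 14.3.2 records adverse events until the final follow-up visit. Section 15.2.4 plans incidence by system organ class and preferred term, with no cut-off date.

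**Antibodies.** Anti-BT063 is sampled at Week 20 ("anti-islet cells, anti-CCP, and Coombs test), and anti-BT063 antibodies", Section 13.1.13) and Week 28 ("and anti-BT063 antibodies; as well as retention samples for immunological status and EBV and CMV serology", Section 13.1.14). Sections 2 and 7 list immunogenicity as a secondary objective.

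**The concern.** Safety and tolerability are the primary objective of both parts, and the one phrase that fixes the period of the primary endpoint joins a visit name and a week that do not belong together. The name points to the end of the trial (Week 28); the number points to End of Treatment (Week 14). The objectives in Section 7 and the safety analysis in Section 15.2.4 give no window, so nothing else in the protocol settles it.

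The choice has some substance. BT063 is a long-lived antibody, so exposure continues well past Week 14. Section 13.5.2.2 classes mouth ulcers as an identified risk, and Section 14.1.2.1 makes them an event of special interest ("Aphthous mouth ulcers (new, recurrent or aggravation of pre-existing lesions"). The dose justification in Section 11.1.3 reports a late case: "After recurrence of mouth ulcers 43 days after the 100 mg BT063 dose in the first subject of the 100 mg cohort". If the window is left unclear, it could be chosen after late events are known.

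**Working it through.** **Inputs.** Dose days 0, 7, 14, 28, 42, 56, 70, 84 (Section 13.1); End of Treatment Day 98±2 (13.1.12); last scheduled visit Day 196 (13.1.14); half-life 20 to 26 days, from single doses in healthy subjects (11.1.3); participation up to 32 weeks (13.2).

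**1. The plan's own calendar.** Screening 4 + treatment 12 + follow-up 16 = 32 weeks, as Section 13.2 states. After baseline, 12 + 16 = 28 weeks, and 28 × 7 = Day 196. The last dose is at Week 12; 12 + 2 = Week 14, and 14 × 7 = Day 98. The schedule is consistent with itself; only the endpoint's visit label disagrees with it.

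**2. Gap between the two readings** (completer, nominal days).
- Length: 196 − 98 = 98 days.
- Share of the treatment-emergent period inside Week 14: 98/196 = 50%.
- Share of the time after the last dose inside Week 14: (98 − 84)/(196 − 84) = 14/112 = 12.5%.
- Under a Week 28 reading both shares are 100%. For a subject who terminates early and whose Visit 12 is the last visit, the two windows coincide.

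**3. Exposure when the Week 14 window closes.** Assuming one-exponential decay, the fraction of the drug present after the last dose that remains is 2^(−days since Day 84 / half-life).

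| Day | Half-life 20 days | Half-life 26 days |
|---|---|---|
| 98 | 2^(−14/20) = 61.6% | 2^(−14/26) = 68.9% |
| 140 | 2^(−56/20) = 14.4% | 2^(−56/26) = 22.5% |
| 196 | 2^(−112/20) = 2.1% | 2^(−112/26) = 5.0% |

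**4. Illustration with the 43-day lag.** Adding 43 to each dose day gives Days 43, 50, 57, 71, 85, 99, 113 and 127. Three of eight fall after nominal Day 98, and two of eight after Day 100, the end of the visit window. After the last dose the event falls on Day 127, during follow-up. This is one recurrence after a single 100 mg dose, not a rate.

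**5. Antibody samples.** After baseline, Section 13.1 schedules anti-BT063 at Weeks 4, 8, 14, 20 and 28. Two of five (Weeks 20 and 28) lie outside a Week 14 endpoint.

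**The case against.** The best answer is that this is a one-word slip, Trial for Treatment. Week 14 is printed both times, the efficacy endpoints name Week 28 where it is meant, the Part I objective concerns three months of treatment, and the interim analysis is triggered at Week 14. A primary window shorter than the treatment-emergent period is a legitimate choice, and analysis detail belongs in a statistical analysis plan that is not at hand. Most of this stands: Week 14 is the likelier meaning, and a short window is no error in itself. What does not fall away is that the protocol itself states its primary endpoint with a visit that does not exist, and leaves the relation to its own treatment-emergent period unstated.

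Three stronger readings are tempting, and the documents do not support them.
- **Late events are lost or dropped from the safety analysis.** They are not: Section 14.3.2 records them to final follow-up, Section 15.2.4 has no cut-off, and Section 8.1 brings available follow-up data into the interim analysis.
- **The primary endpoint omits antibody data that it should contain.** Anti-BT063 sits in the second safety entry and serves the secondary immunogenicity objective; it is not part of the primary adverse event endpoint.
- **The 43-day case shows that mouth ulcers would be missed.** It is a single recurrence in one healthy subject at twice the Part I dose. Incidence counts affected subjects, so an earlier episode in the same subject would already count, and events of special interest are reported within 24 hours whatever the window.

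**Conclusion.** The concern holds as a defect in how the primary endpoint is defined. The label contradicts the visit schedule, and no other section supplies the window. On the likelier Week 14 reading, the endpoint ends 98 days before the protocol's own treatment-emergent period and covers 12.5% of the time after the last dose, with roughly 62% to 69% of the drug present after that dose still there when it closes. Data collection is unaffected. Because the analysis is descriptive, with no tests and no sample size calculation (Sections 15.1 and 15.2.2), neither power nor error rates change.

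The day counts assume a completer at nominal visit days. The exposure figures assume one-exponential decay and that the healthy-subject half-life carries over to these patients. Week 28 is the last scheduled visit; Section 14.3.4.1 allows some subjects a further safety visit up to two weeks later. The point is worth correcting because it concerns the primary endpoint and costs little, not because a result would be invalid.

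**What to change.** 1. In both safety entries of the synopsis, rename the closing visit to End of Treatment Visit (Week 14).
2. State there that adverse event incidence is also reported from first dose to the last study visit (Week 28), the Section 14.3.1 period, beside the Week 14 result.
3. Separately, let the anti-BT063 endpoint include the Week 20 and Week 28 samples, since it serves the immunogenicity objective.
4. Leave unchanged the parameters whose last scheduled result is at Week 14: ECG, thyroid hormones, faecal occult blood, and infection serology (only retention samples are taken at Week 28).

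The change is wording only, with no new visit or sample. Its costs are that the full-window result is complete 28 − 14 = 14 weeks later for each subject, is incomplete for later-enrolled subjects at the interim analysis, and is more affected by the medication changes that Section 11.5 and Table 11.1 allow during follow-up. Keeping the Week 14 result beside it deals with all three.
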